## Introduction

The goal of the analysis described in this document is to use data to be collected through an online experiment to examine the impact of different front-of-package label types and contents on outcomes related to weight stigma and label effectiveness. This document pre-specifies our planned analytic approach prior to data collection.

## Study Protocol

Participants will complete an online randomized experiment programmed in Qualtrics. After providing informed consent and completing an initial parent experiment on alcohol messages, participants will be randomly assigned to view 1 of 4 types of front-of-package labels for sugar-sweetened beverages: neutral control labels, nutrient warning labels, text-only health warning labels, or graphic warning labels. In random order, they will view and rate two versions of their assigned label type on perceived weight stigmatization (primary outcome) and perceived message effectiveness (secondary outcome). The two versions will differ only on whether their content references calories or obesity (i.e., the modified version will not reference either). After rating each version of the label, participants will complete measures of weight bias (secondary outcome) and demographic characteristics.

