## Main Analyses

We will use a two-sided critical alpha of 0.05 to conduct all statistical tests. All confidence intervals presented will use a 95% confidence level. Analyses of the primary and secondary outcomes will include all participants according to the trial arm to which they were randomized. We will use complete case analysis to handle any missing data.

To prepare the data, we will verify that Cronbach's alpha for all scales is sufficient ( $\geq 0.7$ ) and, if so, we will average items to create a mean score on each scale for each

participant. If Cronbach's alpha is not sufficient (<0.7), we will drop items as necessary to improve reliability or treat items as separate constructs.

We will first descriptively report unadjusted means for the primary and secondary outcomes for each experimental arm. To test H1 and H2 (model 1) and H3 (model 2), we will fit separate mixed-effects models with random intercepts to account for repeated measures within participants. These models will include indicator variables for label type (i.e., nutrients, text-only, and graphic - the control label type will be omitted as the referent group), an indicator variable for label version (i.e., regular vs. modified), and interaction terms between label type and label version (i.e., nutrients\*modified, text-only\*modified, and graphic\*modified). To test H4 (model 3), we will fit a linear model including only indicators for label type.

If the interaction terms in models 1 and 2 are not significant, after fitting models 1-3, we will use these models to estimate the main average differential effects of label types (i.e., differences in predicted means between label types averaging between the two version of each label). We will obtain the effect of each label type vs. control, as well as of nutrient vs. text-only, text-only vs. graphic, and nutrient vs. graphic label types. If, in turn, the interaction terms in models 1 and 2 are significant, after fitting models 1 and 2, we will estimate the average differential effects of label types and report them separately for each version of the labels (i.e., we will present differences by label type separately for regular labels and for modified labels). We will not adjust the p-value for each label type compared to control, but will adjust for multiple tests for the three additional pairwise comparisons using the Bonferroni-Holm correction.

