## **Sample Size and Power**

This study will occur in a survey that will follow a parent experiment about alcohol messages. The total sample size (~2,500 participants) was calculated based on the primary outcomes of the parent experiment.

Using G\*Power3.1 and specifying a between-within subjects ANOVA (which should most closely approximate the proposed mixed linear model), we determined the

minimum effect size we would be able to detect on our primary outcome with this pre-determined sample size. With 80% power, a critical alpha of 0.05, four conditions, and two repeated measures, we would be able to detect an effect of  $f=0.057$  (equivalent to  $d=0.11$ ) or larger for the between-subjects factor, and  $f=0.028$  (equivalent to  $d=0.06$ ) or larger for the within-subjects factor. Given that a previous study to analyze the effect of FOPLs on perceived weight stigmatization obtained an effect size of  $d=0.25$  comparing nutrient warnings to control, this study's sample should be sufficiently large to detect an even smaller effect when comparing between nutrient warnings and text-only health warnings, which we expect to be the smallest effect.

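### Parent-experiment condition is used in no planned analysis; adding it to models 1–3, with one exploratory interaction test per model, is a cheap improvement and not the repair of an error

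*Combined protocol and SAP*

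**What the plan says.** The Study Protocol section fixes the order of events: "After providing informed consent and completing an initial parent experiment on alcohol messages, participants will be randomly assigned to view 1 of 4 types". Sample Size and Power confirms it, "This study will occur in a survey that will follow a parent experiment about alcohol messages", and adds that the parent study set the sample: "The total sample size (~2,500 participants) was calculated based on the primary outcomes of the parent experiment".

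Under Main Analyses, models 1 and 2 are random-intercept models. "These models will include indicator variables for label type", and beyond that they hold label version and the type-by-version interaction. For model 3, "we will fit a linear model including only indicators for label type". The moderators under Exploratory Analyses are gender, age, race/ethnicity and perceived weight status, examined for the primary outcome only.

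Parent-experiment condition does not appear as a covariate, allocation factor, moderator or sensitivity analysis, and carry-over is not mentioned. The document also does not describe the parent arms, say that they were randomised, or give the interval between the two parts.

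**The concern.** The parent task resembles the label task: messages about one kind of drink come before ratings of labels for another, and one rated outcome is how effective a message seems. Prior exposure could plausibly move the general level of the ratings, and could also change how far a graphic warning stands apart from a neutral control. The document offers no evidence for or against either effect.

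Two things would be at stake. If parent condition shifts rating levels, that variance stays in the error term of the between-person contrasts (H1, H3, H4), although it comes from a factor fixed before label assignment. If parent condition changes the contrasts themselves, the reported label effects are averages over whatever alcohol messages were seen, and no planned analysis would show how far they depend on them.

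**Working it through.** **Inputs from the plan.** N of about 2,500, four label types, two ratings per person, two-sided alpha 0.05, 80% power; detectable f=0.057 between subjects and f=0.028 within subjects; d=0.25 for nutrient warning against control in a previous study.

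**Assumptions.** Equal allocation (2500/4 = 625 per label type); within-person correlation ρ=0.5; number of parent arms and share of variance explained (R²) over a range. The plan gives none of these.

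**1. The plan's own figures.** With the noncentral F, λ = f²·N·2/(1+ρ) on 3 and 2,496 df between subjects, and λ = f²·N·2/(1−ρ) on 1 and 2,496 df within subjects. At ρ=0.5 the detectable values are f=0.0572 and f=0.0280, and power at the stated 0.057 and 0.028 is 79.6% and 79.9%. Both reproduce at ρ=0.5; correlations of 0, 0.3, 0.7, 0.8 and 0.9 do not reproduce them.

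**2. Validity with parent arm left out.** Simulation of a single rating, two label arms of 625, two parent arms, 4,000 replicates per case. With parent effects of 0, 0.2 and 0.5 SD, and with 0.5 SD plus a 0.3 SD label-by-parent interaction averaging to zero, the mean error of the label contrast was at most 0.001 and type I error was 4.6% to 5.3%.

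**3. Precision gained by the covariate.** The standard error is multiplied by √(1−R²).

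| Assumed R² | SE reduction | Effective sample, 1/(1−R²) | Detectable f, 0.0572·√(1−R²) |
|---|---|---|---|
| 1% | 0.5% | +1.0% | 0.0569 |
| 3% | 1.5% | +3.1% | 0.0564 |
| 5% | 2.5% | +5.3% | 0.0558 |

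For scale, two equal parent arms differing by d=0.2 give R² of about 1.0% for a single rating, (0.1)²/(1+0.1²), or 1.3% for the mean of two ratings, 0.1²/(0.75+0.1²). The version effect in H2 is a within-person difference. A main effect of parent arm cancels from it, so it gains essentially nothing.

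**4. Sensitivity of a carry-over check.** For one label contrast compared between two equal parent arms there are 625/2 = 312.5 people per cell.

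- Single measure (weight bias): 2.80·√(4/312.5) = 2.80·√(8/625) = 0.317 SD.
- Mean of two ratings: 0.317·√((1+0.5)/2) = 0.274 SD of a single rating.
- Three or four parent arms, comparing two of them: 0.34 or 0.39 SD on the mean of two ratings.

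These are 1-df figures. A joint test with two parent arms has 3 df and needs a noncentrality of 10.92 instead of 7.85, a factor of √(10.92/7.85) = 1.18. If two label types depart by equal and opposite amounts and the others do not depart, the requirement becomes 0.274·1.18 = 0.32 SD. If one label type alone departs from the other three, the noncentrality is 1.5 times as large for the same contrast, and the requirement is 0.32/√1.5 = 0.26 SD.

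**5. What an interaction of that size means.** Around a pooled effect of 0.25, an interaction of 0.27 gives 0.25 ± 0.135, or 0.385 and 0.115: same direction, neither erased. Around a pooled 0.11 (the plan's stated detectable d), an interaction of 2·0.11 = 0.22 would erase the effect in one arm, yet power to detect it is only about 61% (standard error 0.274/2.80 = 0.098; 0.22/0.098 − 1.96 = 0.285).

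**6. False alarms.** Three independent tests at 0.05 give 1 − 0.95³ = 14%.

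**The case against.** The strongest reply is that the plan already answers the questions it asks. H1, H3 and H4 concern average differences between label types, randomisation after the parent experiment delivers these without bias, and whether a contrast holds within each parent condition is a question that no hypothesis poses. This stands, and it is why the point is an improvement only.

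The precision gain is small at N of about 2,500; this stands too. That alcohol messages alter weight-stigma ratings of beverage labels is conjecture, and the check is too weak to rule it out; both are correct. What remains is that the covariate is harmless, fixed before label assignment and, if the parent study has arms, should already be on file.

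A reader might infer more than the document supports:

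- *That omitting parent condition biases or invalidates the label contrasts.* It does not (step 2).
- *That the parent arms are known to be randomised and the labels follow within minutes.* The document says only that the parent study is an experiment and comes first.
- *That comparing parent arms would settle the matter of carry-over.* Nobody skips the parent experiment, so an effect shared by all its arms cannot be seen.
- *That the check would pick up exactly the carry-over that changes conclusions.* Step 5 shows otherwise in both directions: a detectable interaction need not overturn a 0.25 effect, and one that erases a smaller effect may be missed.

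**Conclusion.** The gap is confirmed: everyone completes the parent experiment first, and no planned model uses its condition. It is not an error. The consequence is a slightly larger standard error for H1, H3 and H4 than necessary (about 0.5% to 2.5%, on an assumed R² of 1% to 5%) and no view of whether label contrasts differ by parent condition. The recommendation depends on the parent experiment having randomised arms, which the sponsor can confirm. The sensitivity figures also rest on equal allocation, a correlation of 0.5 and two equal parent arms unless stated otherwise.

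**What to change.** If the parent experiment has randomised arms:

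1. Add parent-arm indicators as fixed covariates to models 1, 2 and 3.
2. Pre-specify one test of label type by parent arm per model, labelled exploratory. Show the label contrasts by parent arm descriptively beside the pooled contrasts, which remain the primary result whatever the test shows.
3. State the limits in the SAP: the test addresses only differential carry-over, its sensitivity is as in step 4 of the working, and a null result does not exclude carry-over.
4. Optionally, allocate label type evenly within parent arm in Qualtrics. This adds little: at the 95% limit, chance imbalance moves a contrast by about 1.96·√(0.25·2/625)·0.2 = 0.011 SD for a parent effect of 0.2 SD, and the unadjusted standard error already covers that.

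The cost is SAP wording, a few degrees of freedom out of about 2,500 participants, and up to about a 14% chance of at least one false alarm across the three tests if they are independent. No new data and no larger sample are needed. The Introduction says the plan is fixed before data collection, so the change should be made then; added later, the interaction tests would be post hoc.

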## Hypotheses

Primary outcome: We hypothesize that graphic health warnings will be perceived as most stigmatizing, followed respectively by text-only health warnings, nutrient warnings, and control labels (H1). We also hypothesize that, for all label types, the modified version will be perceived as less stigmatizing than the regular version of the same label (H2).

Secondary outcomes: We hypothesize that graphic health warnings will be perceived as most effective, followed respectively by text-only health warnings, nutrient warnings, and control labels (H3). We also hypothesize that graphic health warnings will elicit the most weight bias, followed respectively by text-only health warnings, nutrient warnings, and control labels (H4).

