## **Exploratory Analyses**

We will examine whether participant characteristics (i.e., gender, age, race/ethnicity, and perceived weight status) moderate the effect of label type (compared to control) on the primary outcome. If the main analysis (model 1) reveals that there is no significant interaction by label type and label version, we will fit a series of mixed-effects models with random intercepts (one for each potential moderator) including label type, label version, the moderator, two-way interactions between label type and label version, and two-way interactions between label type and the moderator. If, in turn, the main analysis (model 1) reveals a significant interaction by label type and label version, we will run separate moderation models for regular labels and for modified labels. We will consider moderation to be supported if the interaction terms between label types and the moderator (in either scenario) are statistically significant, and we will probe such significant interactions by calculating the marginal effect of label types on the outcome at different levels of the moderating variables. We will use Wald tests for categorical moderators with more than 2 categories.

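### Models 1 and 2 leave out the randomised viewing position, and no analysis reports first ratings alone, so some precision is lost and the size of the version effect (H2) cannot be checked against a label seen alone

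*Combined protocol and SAP*

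**What the plan says.** The Study Protocol section assigns each participant to one of four label types and then has them rate both versions of it: "In random order, they will view and rate two versions of their assigned label type". On content it states: "The two versions will differ only on whether their content references calories or obesity". H2, on the primary outcome, is that "for all label types, the modified version will be perceived as less stigmatizing than the regular version of the same label".

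Under Main Analyses, models 1 and 2 have a random intercept, indicators for label type, "an indicator variable for label version (i.e., regular vs. modified), and interaction terms between label type and label version". No term represents viewing position or order. The planned descriptive means are by experimental arm. Under Exploratory Analyses the moderators are four participant characteristics, examined as moderators of label type and not of version. Sample Size and Power gives f=0.028 (d=0.06) "or larger for the within-subjects factor" and does not mention order. No section says that the presentation order will be saved, or plans an estimate from first ratings only.

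**The concern.** Within a label type the version comparison is a two-period crossover: half the participants, if the orders are balanced, see the regular label first and half the modified one. Two separate matters follow.

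- **Position.** If second ratings run generally higher or lower than first ratings, that shift goes into the residual when position is not modelled. The trial randomises the factor and then does not use it.
- **Comparison with the first label.** The two labels are near-identical, so the second may be rated against the first. The paired version effect is then not the effect a person would show on seeing one label alone. The plan does not say which of the two H2 concerns. A participant's first rating cannot be affected by the other version, but the plan never reports first ratings separately.

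At stake are a little precision and how the size of the H2 effect can be read.

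**Working it through.** **Inputs.** From Sample Size and Power: N about 2,500, four conditions, two ratings, 80% power, f=0.057 between and f=0.028 within. From Main Analyses: two-sided alpha 0.05. Assumed: equal allocation (2,500/4 = 625 per type), equal orders, unit SD, and the sizes of the position shift, the true effect and the pull. The within-person correlation ρ is not stated.

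**1. The plan's own figures.** With noncentral F and m=2:
- Between: λ = f²·N·m/(1+ρ). At ρ=0.5 this is 0.057² × 5,000/1.5 = 10.83, power 79.6%.
- Within: λ = f²·N·m/(1−ρ). At ρ=0.5 this is 0.028² × 5,000/0.5 = 7.84, power 79.9%.

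Both figures reproduce at ρ=0.5. They do not reproduce jointly at 0.3 or 0.7, so 0.5 is used below. It recovers a planning input and is not evidence about the data.

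**2. Position.** Let τ be the modified-minus-regular effect and π the shift on second viewing. The paired difference has mean τ+π when regular comes first and τ−π when modified comes first. With equal orders the average is τ, so there is no bias. If position is not modelled, the variance of the difference is 2(1−ρ)+π², a ratio of 1 + π²/(2(1−ρ)). With π = 0.2:
- ρ=0.3: 1 + 0.04/1.4 = 1.03
- ρ=0.5: 1 + 0.04/1.0 = 1.04
- ρ=0.8: 1 + 0.04/0.4 = 1.10

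At ρ=0.5 the standard error rises by √1.04 − 1, about 2%.

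**3. Pull toward one's own first rating.** Let the second rating move a share a toward the first. If regular (R) is first, the modified rating M becomes (1−a)M + aR, and the difference is (1−a)(M−R). If modified is first, the difference is again (1−a)(M−R). Every paired difference is scaled by (1−a). Mean and SD shrink together, and the test statistic is unchanged when a is the same in all types.

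Take an illustrative true effect of 0.1426 SD in every type, chosen because it gives 80% power for all four types at ρ=0.5. Then:
- a=0.2: 0.8 × 0.1426 = 0.114
- a=0.4: 0.6 × 0.1426 = 0.086

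In simulation (625 per type, ρ=0.5) the power for all four types was 81%, 79% and 81% at a = 0, 0.2 and 0.4. The first-rating estimate stayed at about 0.14.

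**4. Precision of the first-rating estimate.** This is a between-person comparison of those who saw modified first with those who saw regular first.
- Per type: √(2/312.5) = 0.080, against a paired SE of √(2 × 0.5/625) = 0.040.
- Overall: √(2/1,250) = 0.040, against a paired SE of √(2 × 0.5/2,500) = 0.020.

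The gap between the first-rating and paired estimates has SE √(0.080² − 0.040²) = 0.069 per type and √(0.040² − 0.020²) = 0.035 overall. A gap of 0.03, 0.06 or 0.12 would be detected in about 7%, 14% or 41% of studies per type, and 14%, 41% or 93% overall. The pulls in step 3 give gaps of 0.1426 − 0.1141 = 0.029 and 0.1426 − 0.0856 = 0.057.

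**5. What a position term can show.** With two versions and two orders, a version effect that differs by order is algebraically the position effect. Carryover that is unequal between the versions appears instead as a difference between the two order groups. A position term improves precision but does not reveal carryover.

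**The case against.** The strongest reply is that randomising the order already does what is needed: a pure position shift cannot bias H2, and the lost precision is small. That stands. So does a second point: under the pull in step 3 the H2 tests are essentially unaffected, and only the estimate shrinks. A third is that the supporting estimate is weak within a single type, where only large carryover would show. That also stands, and it is why the estimate is proposed for description and not as a test.

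A reader might infer more, and the documents do not support it:

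- **That leaving out order biases H2.** Step 2 shows that it does not for a position shift.
- **That comparison between the labels would cost H2 its power.** That requires group means to shift while individual variability stays fixed, which is a different mechanism from people moving toward their own first rating.
- **That H2 could be falsely supported.** With no true effect, a proportional pull or push creates none. An assumed carryover difference of 0.06, 0.12 or 0.24 SD between versions would make one given type significant in about 12%, 32% or 85% of studies at ρ=0.5. These figures assume an unequal carryover for which the documents give neither a mechanism nor a size.
- **That carryover will drive the type-by-version interaction**, which decides whether "we will estimate the average differential effects of label types and report them separately for each version of the labels". That needs carryover to differ by label type, and the documents give no ground for assuming so.

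**Conclusion.** The point holds as a modest one. The omission is complete: no section models viewing position or reports first ratings alone. Its certain consequence is a small loss of precision whenever a position shift exists: about 4% in variance for an assumed 0.2 SD shift at correlation 0.5, and about 3% to 10% for correlations 0.3 to 0.8. Its possible consequence is that the reported version effect differs in size from that of a label seen alone, for example 0.114 or 0.086 in place of an assumed 0.143 SD, with significance materially unchanged. The shift, the true effect and the pull are all assumptions, as are equal allocation and equal orders. No bias is shown. The point bears on how large an H2 effect the trial can report and how that size is interpreted, not on whether the H2 test is valid.

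**What to change.** Suggested wording: *The presentation order of the two versions will be saved for each participant. Models 1 and 2 will include an indicator for viewing position (first, second) to improve precision. As a supporting analysis for perceived weight stigmatization, we will report the regular-versus-modified difference from each participant's first-rated label only, overall (equal weight per label type) and by label type, with 95% CIs. The paired analysis remains primary. The supporting estimate is not a gate, and a non-significant first-rating result does not override the primary result.*

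The position term should not be described as a carryover check. A sentence saying whether H2 concerns a label seen alone or beside its counterpart would also help.

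The cost is one extra coefficient in each of two models and one table. No hypothesis, sample size or primary test changes. The Introduction states: "This document pre-specifies our planned analytic approach prior to data collection". Saving the order can therefore still be specified. The downside is imprecision: 95% half-widths are about 1.96 × 0.040 = 0.08 SD overall and 1.96 × 0.080 = 0.16 SD per type, so the overall figure is the informative one.

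### Perceived weight status is tested as a moderator but appears to be self-rated after label exposure, so a significant interaction need not mean true moderation (minor; exploratory analysis only)

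*Combined protocol and SAP*

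**What the plan says.** The Study Protocol section gives the order of the session. Label assignment follows the parent study: "After providing informed consent and completing an initial parent experiment on alcohol messages, participants will be randomly assigned". Participants then view and rate the two versions of their assigned label type. The personal measures come last, once both versions have been rated: "participants will complete measures of weight bias (secondary outcome) and demographic characteristics". No other collection of personal characteristics is described.

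The Exploratory Analyses section asks whether "participant characteristics (i.e., gender, age, race/ethnicity, and perceived weight status) moderate the effect of label type (compared to control) on the primary outcome". The decision rule is: "We will consider moderation to be supported if the interaction terms between label types and the moderator (in either scenario) are statistically significant". Significant interactions are then probed by estimating label effects at different levels of the moderator.

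Neither section says when perceived weight status is asked, limits moderators to values recorded before exposure, or plans to compare the moderator across arms.

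**The concern.** Randomisation makes the four label groups comparable overall. It keeps them comparable within levels of a moderator only if label type cannot change who falls into each level. Age, gender and race/ethnicity meet that condition for practical purposes. A self-rating of one's own weight may not, if it is given after labels that can mention calories or obesity and in the same block as weight bias items. The plan itself expects label type to move a weight-related attitude: H4 predicts that "graphic health warnings will elicit the most weight bias".

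If a graphic label leads some participants to call themselves overweight who would otherwise not have done so, the overweight group in that arm is a different mix of people from the overweight group under control. When the people who move are also atypical raters of stigma, the label contrast differs between weight groups even though the label acts equally on everyone. The decision rule would read this as moderation. At stake is one exploratory conclusion about whether label effects depend on how people see their own weight.

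**Working it through.** **1. The plan's own figures.** The Sample Size and Power section gives detectable effects of f = 0.057 (between) and f = 0.028 (within) for about 2,500 participants, four conditions, two measures and 80% power. It does not state the correlation ρ between the two ratings.
- Between: λ = f²·N·m/(1 + (m−1)ρ). With ρ = 0.5, 0.057² × 2,500 × 2 / 1.5 = 10.8; power 79.6%.
- Within: λ = f²·N·m/(1−ρ) = 0.028² × 2,500 × 2 / 0.5 = 7.84; power 79.9%.

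Both figures reproduce at ρ = 0.5. At ρ = 0 the detectable values would be 0.047 and 0.040, and at ρ = 0.8 they would be 0.063 and 0.018. So ρ = 0.5 is used below. These figures do not bear on timing.

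**2. Size of a false interaction, two weight groups, graphic versus control.** Only the total sample and alpha come from the documents. The rest is assumed:
- 2,500 / 4 = 625 per arm (equal allocation);
- share p = 0.45 calling themselves overweight without label influence;
- no true moderation, and equal mean stigma ratings in the two weight groups before anyone moves;
- the graphic label moves a share m of all participants into the overweight group, and these people rate stigma g SD above the average of the group they leave.

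Moving them raises the overweight mean by mg/(p+m) and lowers the other group's mean by mg/(1−p−m). The false interaction is the sum:

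bias = mg/(p+m) + mg/(1−p−m).

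The mean of two ratings with correlation 0.5 has variance (1 + 0.5)/2 = 0.75. With 625 × 0.45 = 281.25 and 625 × 0.55 = 343.75 per group:

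SE = √0.75 × √(2/281.25 + 2/343.75) = 0.866 × 0.1137 = 0.098 SD.

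| m | g | bias | bias/SE | rejection at two-sided 5% |
|---|---|---|---|---|
| 3% | 0.3 | 0.009/0.48 + 0.009/0.52 = 0.036 | 0.37 | about 6.6% |
| 5% | 0.5 | 0.025/0.50 + 0.025/0.50 = 0.10 | 1.02 | about 17% |
| 8% | 0.5 | 0.04/0.53 + 0.04/0.47 = 0.16 | 1.63 | about 37% |

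With g = 0 the bias is zero whatever m is. If separate models are fitted to each label version, the factor 0.75 becomes 1 and the rejection rates fall somewhat.

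**3. Benchmark.** The interaction detectable at 80% power with this SE is (1.96 + 0.84) × 0.098, about 0.28 SD.

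**4. Check by simulation under a different model.** Settings: 1,000 runs each, 625 per arm, a three-category moderator, and a joint 6-df test of label type by moderator on the participant mean. There was no true moderation. The label shift rose in equal steps from control to graphic. The personal sensitivity loading on the rating (0.5) and the correlation of weight perception with the rating (0 or 0.3) are assumptions.

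| Moderator | Shift in graphic arm | Rejection rate |
|---|---|---|
| Measured before exposure | any | 3.9% to 5.9% |
| After exposure, same shift for everyone | 0 to 0.3 SD | 4.4% to 5.8% |
| After exposure, shift tied to stigma sensitivity | mean 0.1 SD | 7.0% |
| As above | mean 0.2 SD | 17% to 19% |
| As above | mean 0.3 SD | 35% to 37% |

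**5. Can a comparison across arms clear the moderator?** For 45% versus 50% overweight with 625 per arm, SE = √(0.45 × 0.55/625 + 0.50 × 0.50/625) = 0.028. The ratio is 0.05/0.028 = 1.77, and power is about 43%. A shift of the middle size would be missed more often than found.

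**The case against.** The timing is inferred. The Study Protocol section refers to demographics without naming perceived weight status, and the study sits behind a parent survey whose questionnaire is not in the documents. A reader might infer that the plan states the self-rating is taken after the labels; it does not. This stands, and it makes clarification the first step.

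The route to a difference between arms is also less direct than it looks. Stigma ratings and weight bias items are given in every arm. On the versions, the plan says "The two versions will differ only on whether their content references calories or obesity". Read literally, this covers the control label too, so a weight-related reference alone does not separate the arms; any difference must come from format or strength. H4 concerns weight bias, not self-rated weight, and no figure in the documents shows that a brief label view alters the latter. This stands as well: the mechanism is plausible but undemonstrated.

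Two other inferences are tempting. One is that measurement after exposure produces false moderation by itself. It does not, since both calculations give essentially nominal error when the people who move are typical raters or everyone shifts alike. The other is that a bias of 0.10 SD is serious because it is close to the plan's d = 0.11. That figure is the detectable between-subjects effect, not an interaction. Against the detectable interaction of about 0.28 SD, 0.10 is roughly a third.

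Finally, moving the item to the front of the session is not free. Asked before assignment it would be identical in all arms and so could not confound label contrasts. It could still prime stigma ratings generally, and it would alter another study's survey.

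What survives is that the decision rule treats a possibly exposure-affected self-rating like a fixed characteristic, with no check and no caveat.

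**Conclusion.** The point holds as a minor one. As described, the plan would declare moderation by perceived weight status on interaction significance alone, using a self-rating that appears to follow label exposure. False moderation requires two things: label type shifts the self-rating, and those who shift rate stigma differently. If both hold, the assumed range gives error rates from nearly nominal (6.6%) to 37%, with a false interaction of 0.04 to 0.16 SD. The documents supply no value for the share moved, the rating gap or the overweight share, so this range illustrates what could happen and is not an estimate.

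A reader might extend the point to the main results or to the whole moderation section. The documents do not support that. H1 to H4 do not use this variable, and a label is not expected to change gender, age or race/ethnicity.

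**What to change.** In the Exploratory Analyses section:

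1. State when perceived weight status is recorded. If a value from before label assignment exists, for example in the parent survey, use it; the concern then falls away.
2. If it is recorded after label exposure, report its distribution by label type and test it. Do not treat a non-significant test as clearance, given the power of about 43% for a shift from 45% to 50%.
3. In that case, also describe results by weight status as associations conditional on a post-exposure variable, and exempt this variable from the rule that significance establishes moderation.

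Asking the item earlier is an option for the sponsor to weigh against priming and a change to the parent survey; it is not required. The SAP change costs one extra table and a more cautious conclusion for one exploratory moderator.
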